The baseline of LCI will be the most recent visit with non-missing value before the initial administration of study drug in the corresponding Study Period.

- For ECG, the baseline will be defined as the average of the 3 pretreatment measurements on the start of each Study Period.
- For sweat chloride, the values at each visit will be based on the averaged measurements from left and right arms.
 - The current study baseline will be the value at the most recent visit before the first dose of Study 110.
 - The previous study baseline and cumulative study baseline will be the baseline from the previous study, i.e., average of the values at screening and the pretreatment measurement on Day 1 from the previous studies. If only 1 sweat chloride measurement before the first dose is available, that measurement will be considered the baseline.

Absolute Change from baseline: will be calculated as Post baseline value - Baseline value.

Relative change from baseline: will be calculated and expressed in percentages as $100 \times (\text{Post baseline value} - \text{Baseline value}) / \text{Baseline value}$.

Unscheduled Visits: Unscheduled visit measurements will be included in listings, for derivation of visit windows and computation of baseline/last on-treatment visit, and for the analysis of maximum/minimum values and maximum/minimum changes from baseline values.

Visit Windows: Table 13-5 defines the visit window mapping rules to derive the actual visits for the scheduled post-baseline measurements.

Repeated observations within the same visit window

- For all efficacy parameters, if there are multiple measurements within a visit window, the record at the scheduled visit will be used. If there are no measurements at the scheduled visit, then 1) the record closest to the target day will be used; or 2) if there are multiple records with the same distance to the target day, the latest record will be used.
- For all safety parameters, if there are multiple measurements within a visit window, then 1) the record closest to the target day will be used; or 2) if there are multiple records with the same distance to the target day, the latest record will be used.

BMI, weight, and height will follow safety and efficacy windowing rules. For predose spirometry, efficacy windowing rules will be applied. For postdose serial spirometry, analyses will be based on nominal assessment.

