10.3.2.2 Analysis of Secondary Endpoints

10.3.2.2.1 Analysis of Secondary Endpoints

The analysis of secondary efficacy endpoints will be conducted for the Treatment Cohort Period 1 only.

Absolute change from baseline in LCI_{2.5}

The analysis for efficacy endpoints will be focused on within-group comparison and summaries. No between-groups comparisons will be performed.

For Treatment Cohort Period 1, the mixed model repeated measures (MMRM) analysis will be used for the Cumulative Study Period based on the FAS. It will include two treatment groups (L200/I-L/I and P-L/I) using baseline of the Previous Study Period.

The absolute change from previous study baseline (including all measurements at each visit, both on-treatment measurements and measurements after treatment discontinuation), will be included as the dependent variable; treatment group, visit, and treatment-by-visit interaction, as fixed effects; and subject as a random effect with adjustment for previous studies (Study 109 versus Study 011B), weight (<25 kg versus \geq 25 kg), and ppFEV₁ severity (<90 versus \geq 90), both as determined at screening in the previous studies, and previous study baseline LCI_{2.5} as a continuous variable.

In the model, visit will be treated as a class variable, and an unstructured covariance matrix will be assumed to model the within-subject variability. This model imposes no assumptions on the correlational structure and is considered robust. If there is a convergence problem due to the unstructured covariance matrix, the unstructured covariance matrix will be replaced by compound symmetry in the primary analysis. Denominator degrees of freedom for the *F*-test for fixed effects will be estimated using the Kenward-Roger approximation.¹ With a mixed-effects model as the primary analysis model based on restricted maximum likelihood estimation and assuming that conditional on fixed and random effects data are missing at random, no imputation of missing data will be done.

The result obtained from the model will be the treatment effect at each post baseline visit. The estimated mean within-group treatment effect, i.e., Least Square (LS) Means, SE, 95% CI, and a 2-sided within treatment group *P* value, will be provided. The LS means of absolute change from previous study baseline with 95% CI at each visit during the Cumulative Study Period will be plotted by treatment groups (L200/I-L/I and P-L/I).

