The analysis of CFQ-R respiratory domain will be similar to those specified for the MMRM analysis of LCI_{2.5}, with the absolute change from previous study baseline in CFQ-R respiratory domain score at each visit as the dependent variable; and replacing the baseline LCI_{2.5} with baseline CFQ-R respiratory domain score of the previous studies as a continuous covariate. Figure for CFQ-R respiratory domain score will be plotted similar to absolute change in LCI_{2.5} above. Descriptive summary based on the current study baseline for P-L/I, similar to the summary of LCI_{2.5}, will be provided separately.

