The analysis of height and height-for-age Z-score will be similar to those specified for the MMRM analysis of LCI_{2.5}, with the absolute change from previous study baseline in height or height-for-age z-score, respectively, at each visit as the dependent variable; and replacing the baseline LCI_{2.5} with baseline height or height-for-age z-score of the previous studies, respectively, as a continuous covariate. Figure for height and height-for-age Z-score will be

plotted similar to absolute change in LCI_{2.5} above. Descriptive summary based on the current study baseline for P-L/I, similar to the summary of LCI_{2.5}, will be provided separately.

Absolute change from baseline in TSQM domains

For TSQM domains, the analysis will be similar to those specified for the MMRM analysis of LCI_{2.5}, with the absolute change from previous study baseline in each domain at each visit as the dependent variable; and replacing the baseline LCI_{2.5} with domain baseline of the previous studies as a continuous covariate. Descriptive summary based on the current study baseline for P-L/I, similar to the summary of LCI_{2.5}, will be provided separately.

Number of pulmonary exacerbations (109 Subjects Only)

The number of pulmonary exacerbations will be analyzed using negative binomial regression model (PROC GENMOD) with two treatment groups: L200/I-L/I based on 109 FAS including events in the Cumulative Study Period, and P-L/I based on 109 ROS including events in the Current Study Period. All pulmonary exacerbation events in each corresponding Study Period will be included.

The model will include treatment (L200/I-L/I and P-L/I), weight (<25 kg and ≥25 kg) and ppFEV₁ severity at screening of the previous study (<90 versus ≥90). The log of time spent for each Study Period (end date of the Study Period – first dose date of the corresponding Study Period +1) in patient-years will be treated as the offset in this model.

The data during the placebo-controlled period for subjects randomized to the placebo group in Study 109 will be analyzed using a similar negative binomial regression model without the treatment in the model. Note the placebo rate might be slightly different from that estimated in Study 109 final CSR analyses, which included two arms (placebo and active) instead of the placebo arm only in this model.

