	Day 1 ^b	Day 3 (\pm 1 day)	Day 15 (\pm 3 days) and Week 4 (\pm 1 week)	Week 8, Week 16, Week 24, Week 36, Week 48 (\pm 1 week)	Week 12, Week 20 (\pm 1 week)	Week 60, Week 84 (\pm 1 week)	Week 72 (\pm 1 week)	Week 96 ^c (\pm 1 week)		
Informed consent (and assent, if applicable)	X									
Inclusion/exclusion criteria review	X									
Urine β -hCG ^{h,k}	X		X	X	X ^g	X	X	X	X	X
CFQ-R ^l	X		X	Weeks 16, 24, 48			X	X	X ^m	X
TSQM ^l	X		X	Weeks 16, 24, 48			X	X	X ^m	X
Height and weight ^a	X		X	X		X	X	X	X	X
Vital signs ^o	X		X	X		X	X	X	X	X
Pulse oximetry ^o	X		X	X		X	X	X	X	X

- i If a subject returns to the site for the Week 12 and/or Week 20 laboratory assessments, assessment of the subject's status, any AEs, concomitant medications, treatments, and procedures may be done in the clinic and telephone contact will not be required.
- j Pregnancy tests will be performed for all female subjects who are of childbearing potential from the time of the Day 1 Visit or at any point through the Safety Follow-up Visit (Protocol Section 11.7.8).
- k See Protocol Section 11.7.2 for details.
- l All questionnaires should be completed before the start of any other assessments. The CFQ-R (Protocol Section 11.6.5) should be completed first, followed by the TSQM (Protocol Section 11.6.6).
- m Subjects will need to complete the questionnaires at the Early Termination Visit if it has been 2 weeks or more since they last completed the questionnaire.
- n Height and weight will be measured before study drug dosing with shoes off (Protocol Section 11.6.4). BMI will be derived from this assessment.
- o Vital signs and pulse oximetry will be collected before study drug dosing after the subject has been at rest (seated or supine) for at least 5 minutes (Protocol Section 11.7.4).

Statistical Analysis Plan (Methods)
 Vertex Study: VX15-809-110 Protocol V2.0 Dated 15 September 2015

Table 13-1 Study VX15-809-110: Treatment Cohort Period 1

Event/Assessment ^a	Treatment Period										Early Treatment Termination Visit ^{d,e}	Safety Follow-up Visit (4 weeks [\pm 7 days] After Last Dose) ^{d,e}
	Day 1 ^b	Day 3 (\pm 1 day)	Day 15 (\pm 3 days) and Week 4 (\pm 1 week)	Week 8, Week 16, Week 24, Week 36, Week 48 (\pm 1 week)	Week 12, Week 20 (\pm 1 week)	Week 60, Week 84 (\pm 1 week)	Week 72 (\pm 1 week)	Week 96 ^c (\pm 1 week)	X ^{q,r}	X ^{q,r}		
Ophthalmologic examination ^p	X			Week 48 ^q				X ^{q,r}	X ^{q,r}		X	X ^{q,r}
Full physical examination ^s	X							X	X		X	X

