Standard 12-lead ECG ^t	X ^u	X		Weeks 8, 16, 24, 48				X	X		X	X
Serum β -hCG ^{j,k}	X											
Serum chemistry ^{k,v}	X	X		X	X ^{t,w} LFTs only	X ^{t,w} LFTs only		X	X		X	X
Hematology ^k	X	X		X	X ^{t,w} LFTs only	X ^{t,w} LFTs only		X	X		X	X
Coagulation studies ^{s,k}	X	X	X	Weeks 16, 24, 48				X	X		X	X
Urinalysis ^k	X			Weeks 16, 24, 48				X	X		X	X

^p An ophthalmologic examination will be conducted by a licensed ophthalmologist or optometrist (Protocol Section 11.7.6). Subjects with documentation of bilateral lens removal do not need the ophthalmologic examination. If a cataract or lens opacity is identified and determined to be clinically significant by a licensed ophthalmologist or optometrist at the Day 1 examination (also see Footnote b), the subject will be notified. After discussion with the site principal investigator and in collaboration with the Vertex medical monitor, the subject may elect to participate or not to participate in the study. If the subject continues in the study, more frequent ophthalmologic monitoring should be considered. If a cataract or lens opacity is identified and determined to be clinically significant by a licensed ophthalmologist or optometrist after dosing, the subject will be notified. After discussion with the site principal investigator, and in collaboration with the Vertex medical monitor, the subject may elect to continue or discontinue the study. If the subject discontinues study drug, they should complete the Early Treatment Termination Visit and Safety Follow-up Visit (see Protocol Section 8.1.1.3 for Early Treatment Termination). If the subject continues, more frequent ophthalmologic monitoring should be considered.

^q Subjects may complete the ophthalmologic examination within \pm 1 week of the scheduled visit.

^r An ophthalmologic examination will be conducted by a licensed ophthalmologist or optometrist at the Week 96 Visit (or the Early Treatment Termination Visit if the subject does not have a Week 96 Visit) OR the Safety Follow-up Visit (Protocol Section 11.7.6). Subjects with documentation of bilateral lens removal do not need the ophthalmologic examination.

^s Symptom-directed physical examinations will occur at any time during the study if triggered by AEs or if deemed necessary by the investigator (Protocol Section 11.7.4).

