Appendix D Analysis Visit Window Mapping Rules for Efficacy and Safety Measurements

Table 13-5 Visit Window Mapping Rules for Study 110 Visits

Assessments	Study 110 Visit	Target Study Day	Visit Window (in Study Days)	
• Spirometry (see special handling below)	110 Day 15	15	(1, 22]	
	110 Week 4	29	[23, 43]	
	• Weight and height	110 Week 8	57	[44, 85]
		110 Week 16	113	[86, 141]
	• Vital Signs	110 Week 24	169	[142, 211]
		110 Week 36	253	[212, 295]
		110 Week 48	337	[296, 379]
		110 Week 60	421	[380, 463]
		110 Week 72	505	[464, 547]
		110 Week 84	589	[548, 631]
110 Week 96		673	[632, 687]	
110 Follow-up	701	Nominal Visit		
• Labs	110 Day 15	15	(1, 22]	
	○ Chemistry (Except LFT)	29	[23, 43]	
	○ Hematology	57	[44, 85]	
	110 Week 16	113	[86, 141]	
	110 Week 24	169	[142, 211]	
	110 Week 36	253	[212, 295]	
	110 Week 48	337	[296, 421]	
	110 Week 72	505	[422, 589]	
	110 Week 96	673	[590, 687]	
	110 Follow-up	701	Nominal Visit	
• Chemistry (LFT)	110 Day 15	15	(1, 22]	
	110 Week 4	29	[23, 43]	
	110 Week 8	57	[44, 71]	
	110 Week 12	85	[72, 99]	
	110 Week 16	113	[100, 127]	
	110 Week 20	141	[128, 155]	
	110 Week 24	169	[156, 211]	
	110 Week 36	253	[212, 295]	
	110 Week 48	337	[296, 379]	
	110 Week 60	421	[380, 463]	
	110 Week 72	505	[464, 547]	
	110 Week 84	589	[548, 631]	
	110 Week 96	673	[632, 687]	
110 Follow-up	701	Nominal Visit		
• Coagulation	110 Day 15	15	(1, 22]	
• CFQR, TSQM	110 Week 4	29	[23, 71]	
	110 Week 16	113	[72, 141]	

• TSQM	110 Week 24	169	[142, 253]
	110 Week 48	337	[254, 505]
	110 Week 96	673	[506, 687]
	110 Follow-up	701	Nominal Visit
• Urinalysis (including urine microscopy)	110 Week 16	113	(1, 141]
	110 Week 24	169	[142, 253]
	110 Week 48	337	[254, 505]
	110 Week 96	673	[506, 687]
	110 Follow-up	701	Nominal Visit
• Ophthalmologic examination	110 Week 48	337	[254, 505]
	110 Week 96	673	[506, 687]
	110 Follow-up	701	Nominal Visit
• Standard ECG	110 Day 15	15	(1, 22]
	110 Week 4	29	[23, 43]
	110 Week 8	57	[44, 85]
	110 Week 16	113	[86, 141]
	110 Week 24	169	[142, 253]
	110 Week 48	337	[254, 421]
	110 Week 72	505	[422, 589]
	110 Week 96	673	[590, 687]
	110 Follow-up	701	Nominal Visit
• Sweat Chloride	110 Day 15	15	(1, 22]
	110 Week 4	29	[23, 99]
	110 Week 24	169	[100, 421]
	110 Week 96	673	[422, 687]
• LCI	110 Day 15	15	(1, 22]
	110 Week 4	29	[23, 99]
	110 Week 24	169	[100, 253]
	110 Week 48	337	[254, 505]
	110 Week 96	673	[506, 687]

Special handling for spirometry assessments:

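### CFQ-R and TSQM are collected at Week 72 but have no Week 72 analysis window, so those scores normally go unused by visit and can occasionally be counted as Week 48 or Week 96

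*SAP*

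**What the plan says.** **Schedule.** In SAP Appendix A, Table 13-1, the CFQ-R and TSQM rows mark Day 1, Day 15 and Week 4, Weeks 16, 24 and 48, Week 72, Week 96, Early Treatment Termination and Safety Follow-up. Footnote m asks for the questionnaires at early termination only "if it has been 2 weeks or more since they last completed the questionnaire".

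**Windows.** In SAP Appendix D, "Table 13-5 Visit Window Mapping Rules for Study 110 Visits", CFQ-R and TSQM share one block with coagulation. Its rows are Day 15, Weeks 4, 16, 24, 48 and 96, and Follow-up (by nominal visit). There is no Week 72 row. Week 48 is [254, 505] and Week 96 is [506, 687].

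**Selection.** For efficacy parameters, SAP Section 10.1 says "if there are multiple measurements within a visit window, the record at the scheduled visit will be used". If there is no such record, "the record closest to the target day will be used", and ties go to the latest record.

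**Analysis.** The CFQ-R model is an MMRM "with the absolute change from previous study baseline in CFQ-R respiratory domain score at each visit as the dependent variable", and the TSQM model is the same type of model "with the absolute change from previous study baseline in each domain at each visit as the dependent variable". In the MMRM specification, "visit will be treated as a class variable".

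**The concern.** The window table does not match the SAP's own schedule. A planned assessment has no analysis visit of its own, and the boundary between its neighbours lies on its target day. Whether an on-time Week 72 score belongs to Week 48 or to Week 96 then depends on a difference of one day in the visit date.

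The CFQ-R respiratory domain is a named secondary endpoint (SAP Section 6.2), the TSQM domains are other secondary endpoints (Section 6.3), and long-term efficacy and durability form a secondary objective (Section 5.2). Two things are at stake. The first is an intermediate estimate in the second year, for which the data are already collected. The second is the meaning of the Week 48 and Week 96 labels in a model that treats visit as a category and specifies no imputation of missing data.

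The likely source is the shared block. The "Coagulation studies" row of Table 13-1 shows no Week 72 assessment as far as it can be read, so the limits suit coagulation but not the questionnaires.

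**Working it through.** **1. Is Week 72 really scheduled?** Table 13-1 has ten visit columns: Day 1; Day 3; Day 15 and Week 4; Weeks 8 to 48; Weeks 12 and 20; Weeks 60 and 84; Week 72; Week 96; Early Treatment Termination; Safety Follow-up. Each questionnaire row has ten cells: X, blank, X, Weeks 16/24/48, blank, blank, X, X, X with footnote m, X. Footnote m concerns early termination, which fixes that column, so the two X cells before it are Week 72 and Week 96. The reading rests on the SAP table, because the rows of protocol Table 3-1 are broken in the available text and cannot confirm it.

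**2. Reproduce the printed limits.** Appendix A places the Week w visit on Day 7w + 1, so Weeks 4, 16, 24, 48 and 96 have targets 29, 113, 169, 337 and 673. Midpoints of adjacent targets are:

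- (29 + 113)/2 = 71
- (113 + 169)/2 = 141
- (169 + 337)/2 = 253
- (337 + 673)/2 = 505

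These are the upper limits in Table 13-5 for Weeks 4, 16, 24 and 48. They are reproduced only with Week 72 left out. The Week 48 and Week 96 windows are contiguous, so no row has been lost between them. The table has windows for 6 of the 7 planned on-treatment post-baseline visits.

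**3. Place the on-time Week 72 visits.** The target is 7 × 72 + 1 = 505. With ±1 week, on-time visits are Days 498 to 512, which is 15 days.

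| Week 72 visit day | Window | Number of days | Distance from that window's target |
|---|---|---|---|
| 498–505 | Week 48 [254, 505] | 8 | 498 − 337 = 161 to 505 − 337 = 168 |
| 506–512 | Week 96 [506, 687] | 7 | 673 − 512 = 161 to 673 − 506 = 167 |

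**4. Apply the Section 10.1 rule.** An on-time Week 48 score lies on Days 330 to 344 and an on-time Week 96 score on Days 666 to 680, each at most 7 days from target. A Week 72 score is at least 161 days away. Taking the scheduled visit as the one the window is named for, the Week 48 or Week 96 record is selected. The closest-to-target step would make the same choice. The Week 72 score is then unused by visit.

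**5. When the window's own record is missing.** If no closer record exists either, the Week 72 score is selected and carries the Week 48 or Week 96 label. For example, a child has a Week 48 record and stops treatment, with the termination visit less than 2 weeks after the Week 72 questionnaire. Footnote m waives a repeat, and Follow-up is mapped by nominal visit. Assume no other record falls in the Week 96 window. If the Week 72 score is dated Day 506, it is analysed as Week 96. If it is dated Day 505, it falls in the Week 48 window and is unused.

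**6. Gap in the reported profile.** The targets of the reported visits are 673 − 337 = 336 days apart. With Week 72 included, each gap would be 505 − 337 = 673 − 505 = 168 days.

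**7. Limits with Week 72 included.** (337 + 505)/2 = 421 and (505 + 673)/2 = 589. This gives Week 48 [254, 421], Week 72 [422, 589] and Week 96 [590, 687], which Table 13-5 already prints for ECG. On-time Week 48, 72 and 96 visits (Days 330–344, 498–512 and 666–680) each fall in their own window.

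**The case against.** A reader might infer that the SAP leaves the choice undefined when two scheduled records share a window. The documents do not support that. Section 10.1 gives an ordered rule, and in a row labelled Week 48 with target Day 337 the scheduled visit naturally means Week 48. The rule does not expressly mention two protocol-scheduled visits in one window, but that is a gap in wording, and both of its first two steps select the same record.

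Relabelling is also a narrow case. Most children who stop later than Week 72 should have an early-termination questionnaire nearer to Day 673, which would be chosen instead. To be relabelled as Week 48, a child must have no closer record in that window and still attend Week 72.

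Wide windows are usual in this table. For sweat chloride, Week 24 accepts records up to 421 − 169 = 252 days late. A distance of 161 to 168 days is therefore not unusual in itself. The difference here is that the distant record comes from another planned visit for the same measure.

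Week 48 and Week 96 estimates remain, the primary objective is safety, no between-group comparisons are planned (Section 10.3.2.2.1), and P values are nominal (Section 10.3.2.3). Part of the SAP's efficacy section is also not visible: the contents list has a gap between Sections 10.3.2.3 and 10.4, so a further CFQ-R analysis cannot be excluded.

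These arguments limit the size of the point. They do not remove the mismatch between schedule and windows, and no visible text says that it was intended.

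**Conclusion.** The point holds as a mismatch of moderate importance that should be corrected. Week 72 CFQ-R and TSQM scores have no analysis visit. They normally go unused by visit, which leaves 336 days between reported targets. Occasionally they can be analysed as Week 48 or Week 96 when they lie 161 to 168 days from that target. The effect is on by-visit estimates and on the description of durability, not on error control. It would be too strong to say that the durability objective fails.

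The conclusion rests on three assumptions: the column reading of SAP Table 13-1, the natural reading of the Section 10.1 rule, and the absence of a Week 72 analysis in the parts of the SAP that are not visible. The documents do not give the number of children who would be relabelled; it is probably small.

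**What to change.** In Table 13-5, separate CFQ-R/TSQM from the coagulation block and leave the coagulation windows as they are. For CFQ-R/TSQM set Week 48 [254, 421], Week 72 [422, 589] and Week 96 [590, 687]. Keep the Day 15, Week 4, Week 16, Week 24 and Follow-up rows. The furthest record that can count as Week 48 then falls from 168 to 421 − 337 = 84 days after target. For Week 96 it falls from 167 to 673 − 590 = 83 days before target, so some early-termination scores can still be labelled Week 96.

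The cost is one split block, two changed limits and one added row. By-visit tables gain one visit, and no new data are needed. Each CFQ-R and TSQM MMRM also gains a visit: with k visits already in the model, the unstructured covariance gains k + 1 parameters. That slightly raises the chance of a convergence problem and of the compound-symmetry fallback in Section 10.3.2.2.1.

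If leaving out Week 72 was intended, a sentence in Appendix D would be enough. It should say that Week 72 questionnaire scores are not analysed by visit and may not fill the Week 48 or Week 96 slot. This removes the relabelling but gives up the intermediate estimate.
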